## **Summary of potential toxicity in patients**

### **Gastrointestinal system**

Nausea, vomiting, anorexia/decreased appetite, and diarrhea were reported as DLTs in clinical studies with dovitinib. Additionally, they were the top commonly reported AEs for both continuous once daily dosing regimen (N = 155) and 5 days on/2 days off dosing regimen (N = 378 for global, N = 28 for Japan study 1101). Most of these events were mild to moderate (grade 1/2). Grade 3/4 events occurred in less than 10% of patients for both continuous once daily dosing regimen and 5 days on / 2 days off dosing regimen, with an exception of grade 3/4 decreased appetite reported in 14.3% of patients treated in the phase I study in Japan..

Cases of gastrointestinal tract perforation and fistula formation with suspected relationship to the study drug have been reported. Dovitinib inhibits VEGF along with FGFR and PDGF; perforation and fistula formation is a known class effect for VEGF inhibitors.

### **Hematologic events**

Neutropenia was reported as DLTs from dovitinib clinical studies (continuous once daily dosing regimen) in patients with acute myeloid leukemia or multiple myeloma.

Grade 3 and 4 hematological toxicity is generally not common in patients treated with dovitinib for solid tumors. Grade 3 and 4 decrease in neutrophil values were observed in 3.6% and 1.5% of patients in the global Phase I and II studies, in 1.1% and 0.2% of patients in the global Phase III RCC study, in 3.4% and 0.0% of patients in the global Phase II HCC study and in 10.7% and 3.6% in the Japanese phase I study, respectively. Grade 3 and 4 thrombocytopenia is also uncommon, with grade 3 and 4 decrease in platelet values observed in 3.3% and 0.6% of patients in the global Phase I and II studies, in 0.0% of patients in the global Phase III RCC study, in 8.1% and 1.3% of patients in the global Phase II HCC study, in 1.8% and 1.2% in the Phase I BE study and in 3.6% and 0.0% of patients, respectively in the Japanese phase I study. Additionally, grade 3/4 lymphopenia was reported as an adverse event in 21.4% of patients in the Phase I Japan study (17.9% of grade 3 and 3.6% of grade 4) (Table 5-16).

Investigators are advised to follow protocol provided guidelines for hematologic toxicity management, e.g. dose modification, treatment interruption/discontinuation.

### **Hepatic effects**

Delayed recovery from AST/ALT elevations and grade 3 liver function disorder were reported as DLTs in dovitinib phase I clinical studies.

Newly occurring or worsening grade 3 and 4 increase in AST values were observed in 5.6% and 0.3% of patients in the global Phase I and II studies, in 0.2% and 0.0% of patients in the global Phase III RCC study, in 26.2% and 1.3% of patients in the global Phase II HCC study, in 1.8% and 0.0% of patients in the Phase I BE study and in 14.3% and 0.0% of patients in the Japanese phase I study, respectively. Newly occurring or worsening grade 3 and 4 increase in ALT values were observed in 5.3% and 0.5% of patients in the global Phase I and II studies, in 0.2% and 0.0% of patients in the global Phase III RCC study, in 15.4% and 1.3% of patients in the global Phase II HCC study, in 0.0% of patients in the Phase I BE study and in 10.7% and 0.0%, respectively in the Japanese phase I study. ALT/AST increased as an adverse event, regardless of study drug relationship, were common in AST and ALT in the global Phase I and II studies; 3.1% and 2.6% of patients for AST and ALT, respectively, in the global Phase III RCC study; 1.8% and 0.6% of patients for AST and ALT, respectively, in the global Phase I BE study; 25.5% and 18.8% of patients for AST and ALT, respectively, in the global Phase II HCC study and 25 - 28.6% of patients in the Japan study) ([Table 7-1](#), [Table 7-2](#), [Table 7-3](#), [Table 7-4](#) and [Table 7-5](#)). In addition, grade 3/4 ALT/AST increased, regardless of study drug relationship, were reported in 2.4 - 2.9%, 12.1 - 23.5%, and 3.6% for the 5 days on / 2 days off global Phase I and II studies, Phase II HCC study, and Phase I Japan study, respectively. Of note, no patients treated with dovitinib have experienced hepatotoxicity meeting the criteria for Hy's Law, which is considered predictive of severe drug-related hepatocellular injury.

In addition, a fatal case of hepatotoxicity (cholestatic liver injury) was observed in a patient with metastatic breast cancer after approximately one month of treatment with dovitinib; both the cholestatic liver injury and the death were deemed drug-related by the investigator. A review of the safety database for dovitinib showed that no other serious hepatotoxic event with a similar pattern and severity.

Dovitinib inhibits VEGF, as well as FGFR and PDGF. Hepatotoxicity is a known class effect for VEGF inhibitors. Investigators are reminded to evaluate the pattern of liver function test abnormalities and follow the management paradigm in the study protocols to interrupt or discontinue dovitinib treatment. Dovitinib re-challenge should only be considered if the patient's liver function tests return to grade 1 or baseline.

## **Renal system**

No DLTs were reported in the renal system in phase I studies. Grade 3 and 4 increase in creatinine values is not common in patients treated with dovitinib (1.6 and 0.8% of patients in the global Phase I and II studies; 0.0 and 0.6% of patients in the Phase I BE study; 0.7 and 0.0% in the HCC study and no grade 3 or 4 creatinine value increase in the Japanese phase I and Phase III RCC studies.

## **Other reported toxicities**

Increased gamma glutamyltransferase and hypokalemia were the other laboratory DLTs, whereas fatigue/asthenia were the other non-laboratory DLTs reported in. For both dosing schedules (once daily and 5 days on/2 days off), fatigue/asthenia were listed among the commonly reported AEs ( $\geq 10\%$  of patients). In addition, fatigue/asthenia had high incidences among all grade 3/4 events.

Other commonly reported adverse events from both dosing schedules, regardless of study drug relationship, include headache, dyspnea, constipation, pyrexia, cough, dyspepsia, and dry mouth. About 3.9% of patients (n = 16) reported for palmar-plantar erythrodysesthesia syndrome (PPES) in the studies using 5 days on/2 days off dosing schedule (N = 378 global studies, and N = 28 Japan study 1101). Among them, 3 grade 3 events were reported and no grade 4 events were observed. PPES has also been reported with the use of other tyrosine kinase inhibitors.

Serum amylase and triglycerides are monitored in the clinical studies with dovitinib, because their abnormal levels were reported in the preclinical toxicology studies. Newly occurring or worsening grade 3/4 increase in triglycerides were reported in patients who have received dovitinib treatment in clinical trials of the 5 days on/2 days off dosing schedule; 88 with grade 3 and 18 with grade 4.

### **1.2.3 Biomarker Development**

Biomarkers are objectively measured and evaluated indicators of normal biological processes, pathogenic processes and/or pharmacologic responses to a therapeutic intervention.

In preclinical *in vitro* models in the RT114 and RT4 UC cell lines which over-express FGFR3, significant inhibition of FGFR3 signaling and cell growth was observed in association with dovitinib therapy. Furthermore, in an orthotopic model of FGFR3 S249C activating mutation transformed NIH3T3 fibroblast subcutaneous tumor implants, dovitinib significantly inhibited tumor growth. In addition, dovitinib was well tolerated and demonstrated anti-tumor activity in an orthotopic bladder cancer mouse model in tumors over-expressing FGFR3 (2010a). The relative contributions of FGFR3 over-expression versus specific FGFR3 activating mutations in human urothelial carcinoma have not been fully characterized. Therefore as a secondary objective of this trial we aim to characterize pre- and post-treatment bladder tumor FGFR pathway phosphorylation changes, 6-month CR rates, and 1-year RFS rates according to FGFR3 over-expression versus mutation status.

Biomarkers predictive of clinical efficacy and toxicity are emerging for VEGF directed therapies. In a recent randomized placebo-controlled phase III study (ECOG 2100) of paclitaxel plus bevacizumab (a recombinant humanized monoclonal antibody to VEGF) in the first-line treatment of metastatic breast cancer, patients who received bevacizumab demonstrated a significant prolongation of progression free survival (11.8 vs. 5.9 months, HR=0.60 p=0.001) (Miller et al., 2007). When the entire study population was analyzed (n=772), no significant differences in median overall survival were observed between patients who received bevacizumab and those who received placebo (26.7 months vs. 25.2 months, HR 0.88 p=0.15). In a planned biomarker analysis, the breast cancer tumor genotype frequencies of single nucleotide polymorphisms (SNPs) in seven VEGF and VEGF receptor genes were determined from patient formalin fixed paraffin embedded tissue blocks (FFPE). Patients whose tumors possessed a VEGF (-2578 AA) or a VEGF (-1154 AA) genotype had a marked statistically significant improvement in median overall survival in association with bevacizumab therapy (-2578 AA genotype HR 0.58 p=0.023, -1154 AA genotype HR 0.62 p=0.001) (Schneider et al., 2008). Furthermore, significant associations between hypertension and patients with the VEGF (-634 CC) genotype (p=0.005) and the VEGF (-1498 TT) genotype (p=0.022) were also observed. Confirmation of these observations is planned in a prospective large randomized phase III trial testing the role of bevacizumab in addition to standard chemotherapy for breast cancer patients in the adjuvant setting. Lastly, investigators have also observed associations between the development of treatment related hypertension and favorable clinical outcomes in patients treated with VEGF directed therapies (Bono et al., 2011). To date, no predictors of response to VEGF directed therapy have been examined or reported in bladder cancer. Therefore as additional secondary objectives of this trial we plan to assess associations between improved biologic and clinical outcomes according to VEGFR over-expression, host VEGFR mutation, and treatment related hypertension status.

In addition, the ability to detect circulating tumor cells (CTCs) within the peripheral blood of cancer patients is well established (Yu et al., 2011). While promising, the current FDA approved CellSearch® technology has significant limitations including, but not limited to: 1) the need for real time analysis of specimens within 72 hours of collection; 2) the inability to do full genome profiling of CTC DNA/RNA; and 3) the dependence on tumor cells to express the pan-cytokeratin epithelial marker (EpCAM) on their cell surface and hence an inability to detect cells which have undergone epithelial to mesenchymal transformation (EMT). Accordingly, investigators have begun examining more readily available means to identify, quantify, and characterize tumor genomic content circulating within patients. The study of circulating free DNA/RNA (CFDNA/CFRNA) from peripheral blood and urine demonstrated feasibility in early studies (Gormally et al., 2007). A particular advantage of CFDNA/CFRNA platforms is the ability to analyze banked frozen patients samples. As a purely exploratory objective of this trial, we plan to assess the presence of FGFR3 mutations in patient baseline CFRNA from plasma and CFDNA from urine samples.

Lastly, while dovitinib has demonstrated excellent systemic bioavailability in oral form and the bladder epithelium is well vascularized, confirmation of dovitinib reaching its target will greatly enhance the clinical interpretation of patient outcomes at the completion of the study. As such, a final exploratory objective of this trial will be to measure bladder tissue concentrations of dovitinib at the initial post-treatment biopsy.

## **2 Study Purpose/Rationale**

Due to the significant morbidity and quality of life detriments associated with cystectomy, new treatment approaches are clearly needed for BCG-refractory UC patients. Given dovitinib's dual targeting of the VEGFR and FGFR pathways, the preclinical activity of dovitinib in UC cell lines, the convenience of a daily oral administration, and a tolerable side effect profile, a strong rationale exists to test the clinical efficacy of dovitinib in BCG-refractory UC. This is particularly true for patients with tumors harboring FGFR3 mutations or with FGFR3 over-expression.

## **3 Objectives and Endpoints**

### **3.1 Primary Objectives**

- To determine the 6-month complete response rate in BCG-refractory UC patients with FGFR3 mutant or over-expressing tumors treated with dovitinib.

#### **3.1.1 Endpoint for Primary Objectives**

- The 6-month complete response rate is defined as the proportion of patients treated with dovitinib with no evidence of any remaining urothelial carcinoma tumors of any T-stage (including Tis) present within the bladder as assessed by standard of care cystoscopic examination with TURBT and urine cytology performed at 6 months after initiation of study therapy.

NOTE: Patients with residual non-invasive UC tumors with no component of carcinoma in situ (i.e. Ta, T1) at 3-month cystoscopy and TURBT are not considered relapses and will be permitted to continue on dovitinib therapy. If the subsequent 6-month cystoscopy/TURBT, and urine cytology shows no evidence of any remaining urothelial carcinoma in such patients, they will be considered a complete response. Patients with any component of carcinoma in-situ (CIS) at 3-month cystoscopy/TURBT will be considered relapses and will not continue on dovitinib therapy. Any non-invasive UC tumors (i.e. Ta, T1, Tis) at the 6-month or any subsequent cystoscopy/TURBT is

considered relapsed disease. Similarly progression to invasive UC tumors (T2-T4) at any time point is also considered relapsed disease and patients will not continue on dovitinib therapy.

## 3.2 Secondary Objectives

- To determine the 1-year relapse free survival rate in BCG-refractory UC patients treated with dovitinib.
- To determine the rate of progression to muscle-invasive stage (i.e. T2-T4).
- To determine 3- and 6-month partial response rate defined as a reduction in T-stage on post-therapy TURBT (i.e. T1 -> Ta; T1+Tis -> Tis).
- To characterize treatment related toxicity rates assessed by CTCAE v4.0.

### 3.2.1 Endpoint for Secondary Objectives

- The 1-year relapse free survival rate is defined as the proportion of patients treated with dovitinib with no evidence of any remaining urothelial carcinoma tumors at 12 months of follow-up.

**NOTE:** Patients with residual non-invasive UC tumors with no component of carcinoma in situ (i.e. Ta, T1) at 3-month cystoscopy and TURBT are not considered relapses and will be permitted to continue on dovitinib therapy. If the subsequent 6-month cystoscopy/TURBT, and urine cytology shows no evidence of any remaining urothelial carcinoma in such patients, they will be considered a complete response. Patients with any component of carcinoma in-situ (CIS) at 3-month cystoscopy/TURBT will be considered relapses and will not continue on dovitinib therapy. Any non-invasive UC tumors (i.e. Ta, T1, Tis) at the 6-month or any subsequent cystoscopy/TURBT is considered relapsed disease. Similarly progression to invasive UC tumors (T2-T4) at any time point is also considered relapsed disease and patients will not continue on dovitinib therapy.

- The rate of progression to muscle-invasive stage for dovitinib is defined as the proportion of patients with clinical or pathologic progression to muscle-invasive stages (i.e. T2-T4) at any time point on study. Pathologic progression is assessed by histological finding at TURBT or cystectomy. Clinical progression is assessed by clinician's physical exam and findings on radiologic imaging as ordered per the treating physician's discretion.
- The 3- and 6-month partial response rates are defined as the proportion of patients treated with persistent but reduced T-stage tumors on post-therapy TURBT (i.e. T1 -> Ta; T1+Tis -> T1).
- Treatment related toxicity rates will be assessed by CTCAE v4.0.

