
### **1.1.6 Fibroblast Growth Factor Receptor as a Therapeutic Target in UC**

UC carcinogenesis is a multi-step process that affects multiple cellular genes and signaling pathways. Low-grade NMIBC tumors are characterized by mutations in the fibroblast growth factor receptor-3 (FGFR3) and the Harvey rat sarcoma viral oncogene homologue (HRAS) genes (Mitra et al., 2006, Wu, 2005). FGFR3

mutations or over-expression promote FGFR dimerization and constitutive activation of downstream signaling pathways in the absence of ligand in up to 80% of early-stage UC tumors (Table 1) (Knowles, 2008).

**Table 1-1:** FGFR3 mutation and Over-expression Status According to T-stage

	Ta (%)	T1 (%)	T2 (%)
Mutation	67	42	13
Over-expression	13	15	39
Total	80	57	52

While many FGFR3 mutations have been reported, S249C, Y375C, R248C, and G372C account for greater than 95% of all reported mutations (Kompier et al., 2010). These mutations result in a hyperplastic phenotype dominated by frequent tumor recurrences with infrequent progression to muscle-invasive stages. Somatic FGFR3 mutations (see Table 1-2) in exons 7, 10, and 15 will be assessed in FFPE tumor tissues by massively parallel sequencing analysis utilizing the Ion Torrent Personal Genome machine (PGM) and performed in the CLIA-certified Molecular Pathology and Translational Research Laboratory at the Dartmouth Hitchcock Medical Center.

**Table 1-2:** FGFR3 mutations to be analyzed

FGFR3 Mutations
R248C
S249C
G372C
S373C
Y375C
K562E
K562Q
K562M
K562T

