#### **5.1 Inclusion Criteria**

Patients eligible for inclusion in this study have to **meet all** of the following criteria:

1. Histologically confirmed non-muscle invasive urothelial carcinoma of the bladder defined as Ta, T1, or Tis stage. Tumor staging must be confirmed by TURBT performed within 42 days prior to registration.
2. Presence of either an FGFR3 mutation or FGFR3 over-expression within bladder tumor tissue. Somatic FGFR3 mutations (see Table 1-2) in exons 7, 10, and 15 will be assessed in FFPE tumor tissues by massively parallel sequencing analysis utilizing the Ion Torrent Personal Genome Machine (PGM) and performed in the CLIA-certified Molecular Pathology and Translational Research Laboratory at the Dartmouth Hitchcock Medical Center. FGFR3 over-expression will be assessed by standard IHC analysis performed within the Indiana University Simon Cancer Center Immunohistochemistry (IHC) Core Lab.

NOTE: Patients will initially be allowed to enroll if their tumors demonstrate either an FGFR3 mutation or FGFR3 over-expression. However, a minimum of 10 FGFR3

mutation positive patients will be enrolled at study completion. If 10 patients with tumors that are FGFR3 over-expressors but FGFR3 mutation negative are accrued prior to enrolling 10 FGFR3 mutation positive patients, subsequent enrollment will be restricted to patients with tumors that are FGFR3 mutation positive.

3. Documented BCG-refractory disease defined as failure to achieve a tumor free state after at least 2 prior intravesical treatment courses, one of which must have been intravesical BCG therapy.

**NOTE:** There is no maximum limit on the number of prior BCG therapy courses. In addition, there is no maximum limit on the number of prior non-BCG intravesical therapy courses (i.e. gemcitabine, valrubicin, interferon, mitomycin C, etc.).

4. Medically unfit to undergo cystectomy or electively choosing to forego cystectomy

5. ECOG (WHO) performance status 0 or 1 or 2

6. Age  $\geq$  18 years old

7. Patients must have the following laboratory values:

- White blood cell count (WBC)  $\geq$  3.0 K/mm^3
- Absolute neutrophil count (ANC)  $\geq$  1.5 K/mm^3
- Platelets  $\geq$  100 K/mm^3
- Hemoglobin (Hgb)  $\geq$  9 g/dL
- Serum total bilirubin:  $\leq$  1.5 x ULN
- ALT and AST  $\leq$  3.0 x ULN

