## **7.5 Patient Demographics and Other Baseline Characteristics**

At screening/baseline, the following demographic and screening/baseline characteristic data will be collected from all patients:

- Date of birth
- Sex
- Ethnicity
- Race
- Height
- Weight
- Systolic blood pressure
- Diastolic blood pressure
- ECOG performance status
- Cystectomy eligibility status (if ineligible, record reason)
- White blood cell count
- Absolute neutrophil count

- Hemoglobin
- Platelet count
- Creatinine
- AST
- ALT
- Total bilirubin
- Alkaline phosphatase
- Left ventricular ejection fraction
- Charlson comorbidity index (CCI)

The CCI for each patient is determined by summation of relative point values for each patient co-morbidity condition according to the following system:

Conditions assigned 1 point each:

- Myocardial infarct
- Congestive heart failure
- Peripheral vascular disease
- Dementia
- Cerebrovascular disease (CVA with mild or no residual effects or TIA)
- Chronic lung disease
- Connective tissue disease
- Peptic ulcer
- Mild chronic liver disease (i.e. without evidence of portal hypertension, includes chronic hepatitis)
- Diabetes without end-organ damage (excludes diet-controlled alone)

Conditions assigned 2 points each:

- Hemiplegia
- Moderate or severe kidney disease (GFR  $\leq$  60 ml/min by Cockcroft-Gault formula)
- Diabetes with end organ damage (i.e. retinopathy, neuropathy, nephropathy)
- Any cancer (exclude if > 5 years from diagnosis with no active disease)
- Leukemia (acute or chronic)
- Lymphoma

Conditions assigned 3 points each:

- Moderate or severe liver disease (i.e. with evidence of portal hypertension)

Conditions assigned 6 points each:

- Metastatic solid organ cancer
- AIDS

For example, a patient with BCG-refractory urothelial carcinoma (2 pts), type 2 diabetes without end organ damage (1 pt), past history of a non-ST-elevation myocardial infarction (1 pt), with history of chronic obstructive pulmonary disease (1 pt) would have a CCI = 5.

- Bladder tumor stage (Ta, Tis, T1, Ta + Tis, T1 + Tis)
- Number of prior intravesical BCG courses (i.e. BCG x 2 courses → mitomycin C x 1 course → gemcitabine x 1 course = 2 prior BCG courses)
- Number of prior intravesical courses of any type (i.e. BCG x 2 courses → mitomycin C x 1 course → gemcitabine x 1 course = 4 prior intravesical courses)
- Number of prior intravesical agents received (i.e. BCG x 2 courses → mitomycin C x 1 course → gemcitabine = 3 prior agents)

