### **7.10.12.4 Complete Response (CR)**

Complete response (CR) is defined as disappearance of all bladder tumors (of any T-stage), both grossly and microscopically on urine cytology and post-treatment bladder biopsy.

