### **7.10.12.5 Partial Response (PR)**

A partial response (PR) is defined as persistently present, but reduced bladder tumor T-stage on post-treatment bladder biopsy/TURBT in the absence of any new bladder tumors of any stage and in the absence of progression to muscle-invasive stage (i.e.  $\geq T2$ ) of any previously documented bladder tumors. A reduction in the number of bladder tumors but that retains the baseline T-stage does not qualify as a partial response. The following is a list of partial response examples:

T1 → Ta

T1 + Tis → T1

T1 + Tis → Ta

Tis → Ta

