## **10 Statistical Methods and Data Analysis**

### **10.1 General Considerations**

Statistical analysis of this study will be the responsibility of the Department of Biostatistics at IUSM. Parameter estimates and relevant summary statistics will be reported for both efficacy and safety outcomes. Continuous variables will be summarized by means, medians, minima, maxima and standard deviations. Categorical variables will be summarized by frequencies and percentages. Missing data are expected to be rare. For patients that start therapy but do not make it to the primary endpoint evaluation, their 6-month status will be treated as not achieving CR. Consequently, our estimate of 6-month CR rate will be conservative. For secondary outcomes, missing data, if any, will not be imputed and complete-case analysis will be adopted. Additional exploratory analysis will be conducted when appropriate. Changes from the analysis plan will not require an amendment to the protocol unless it changes a significant feature in the protocol.

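### The partial response rate counts Ta-only patients in its denominator although the response rules leave them no way to be a partial responder

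*Combined protocol and SAP*

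**What the plan says.** Section 3.2.1 sets the denominator: "The 3- and 6-month partial response rates are defined as the proportion of patients treated with persistent but reduced T-stage tumors on post-therapy TURBT". No baseline stage is excluded. Section 10.6.2 reports the 3- and 6-month PR rates with 90% Agresti-Coull intervals and names neither an analysis set nor a stage breakdown. Table 3-1 and Section 10.6.1 list PR among the key secondary objectives.

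Section 7.10.12.5 defines a PR as tumor that is "persistently present, but reduced bladder tumor T-stage on post-treatment bladder biopsy/TURBT in the absence of any new bladder tumors of any stage", and without progression to muscle invasion. It adds: "A reduction in the number of bladder tumors but that retains the baseline T-stage does not qualify as a partial response". Its four examples are T1 to Ta, T1+Tis to T1, T1+Tis to Ta, and Tis to Ta. None starts from Ta alone. Section 7.10.12.4 defines CR as "disappearance of all bladder tumors (of any T-stage), both grossly and microscopically on urine cytology and post-treatment bladder biopsy".

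Inclusion criterion 1 (Section 5.1) admits "Histologically confirmed non-muscle invasive urothelial carcinoma of the bladder defined as Ta, T1, or Tis stage". Section 7.5 records Ta alone as a separate baseline category: "Bladder tumor stage (Ta, Tis, T1, Ta + Tis, T1 + Tis".

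On missing data, Section 10.1 states: "For secondary outcomes, missing data, if any, will not be imputed and complete-case analysis will be adopted". The efficacy set in Section 10.2.5 requires one dose and one post-treatment evaluation, without regard to stage.

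**The concern.** A response rate is easiest to read when every patient in the denominator could in principle have responded. Here one eligible group cannot. Take a patient with eight Ta tumors at baseline and a single Ta tumor at 3 months: the disease has shrunk, but the rule does not call this a PR, and the patient still counts in the denominator.

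The reported rate then mixes two things: how often dovitinib lowers the stage where it can be lowered, and what share of enrolled patients had Ta alone. A low figure could reflect weak activity, a large Ta-only share, or both. With only 20 patients the stage mix can move the estimate a good deal. Comparison with another series would also depend on that series having a similar mix.

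**Working it through.** **Step 1. Can a Ta-only patient ever be a PR?** The possible findings at a 3- or 6-month TURBT, set against the definitions:

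| Finding | Classification | PR? |
|---|---|---|
| T0 with negative cytology | CR (7.10.12.4) | No |
| Ta, same number or fewer | Baseline stage retained (7.10.12.5) | No |
| Any Tis component | Not a reduction: 7.10.12.5 lists Tis to Ta as the reduction | No |
| T1 | Higher stage | No |
| T2 or higher | Muscle-invasive progression (7.10.12.6) | No |

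No row gives a PR. T0 does lie below Ta in the staging list of Section 7.10.2.1, but it is a CR. The exact statement is that Ta has no lower T-stage with tumor still present.

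**Step 2. Does another rule remove these patients?** The efficacy set and the complete-case rule drop patients without an evaluation. An evaluated Ta-only patient stays in. The baseline-factor models of Section 10.7.1 cover 6-month CR and 1-year relapse-free survival, not PR.

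**Step 3. The identity.** Let f be the Ta-only share of the denominator and q the PR rate among the other patients. Then

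planned PR rate = (1 − f) × q + f × 0 = (1 − f) × q.

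The documents give neither f nor q. With an assumed q of 40%:

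| Assumed f | Planned rate |
|---|---|
| 10% | 0.90 × 40% = 36% |
| 25% | 0.75 × 40% = 30% |
| 40% | 0.60 × 40% = 24% |
| 50% | 0.50 × 40% = 20% |
| 60% | 0.40 × 40% = 16% |

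**Step 4. Intervals.** The plan states no PR figure to reproduce, so the interval method was checked against Section 10.9. The Agresti-Coull limits are p̃ ± z√(p̃(1 − p̃)/ñ), with ñ = n + z² and p̃ = (x + z²/2)/ñ. With z = 1.645 (two-sided 90%) and n = 10, the lower limits for x = 4, 5 and 6 are 0.193, 0.269 and 0.351, matching the plan's 0.19, 0.27 and 0.35. The same formula with 4 partial responses gives:

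- all 20 patients: 4/20 = 20.0% (8.9% to 38.2%)
- if 5 of the 20 are Ta-only: 4/15 = 26.7% (12.3% to 48.2%)
- if 10 of the 20 are Ta-only: 4/10 = 40.0% (19.3% to 64.9%)

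**Step 5. Does FGFR3 selection change f?** Table 1-1 gives FGFR3 mutation or over-expression in 80% of Ta and 57% of T1 tumors. If s is the Ta share before screening and all other patients are treated as T1, the share after selection is 0.80s / (0.80s + 0.57(1 − s)). For s = 30% this is 0.240/0.639 = 38%; for s = 50% it is 0.400/0.685 = 58%. Both starting shares are assumptions, and the table has no Tis column. This supports a direction, not a size.

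**The case against.** The strongest reply is that the planned rate is a legitimate quantity. It is defined over treated patients and estimates what it says. Excluding a lower tumor count at the same stage is explicit and looks deliberate. On that view this is a preference for a different denominator, not a bias. That stands as far as it goes: the planned rate should be kept. What remains is that it is the only PR rate planned, and it cannot be interpreted without the stage mix.

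Second, the stage mix will be reported. Section 10.3 summarizes baseline disease characteristics for the full analysis set, so a reader could divide the PR count by the patients who are not Ta-only. This recovers the rate only approximately, because complete-case handling can change the denominator at 3 and 6 months, and it gives no planned interval.

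Third, a reader might infer that the PR rate will be understated by some stated percentage, or that FGFR3 selection makes this a Ta-dominated trial. The documents support neither. Table 1-1 gives the alteration frequency within each stage, not the stage distribution among altered tumors. Section 10.8 assumes alterations in only 40% of BCG-refractory tumors, described there as conservative, which is below the table's figures for both Ta and T1. Section 10.7.1 names T1 versus CIS as its example stage contrast. A small f is consistent with all of this.

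Fourth, the definitions beneath any reducible-stage denominator are unsettled. T1+Tis to Tis is the example in Sections 3.2 and 10.6.1, while Sections 3.2.1 and 7.10.12.5 give T1+Tis to T1. Tis to Ta sits awkwardly with the bar on new tumors of any stage. Ta+Tis to Ta is not listed. The note in Section 3.2.1 also makes any tumor at 6 months a relapse, so every 6-month PR is one too. This objection stands and shapes the fix.

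**Conclusion.** The point holds as a matter of definition: a Ta-only patient is a structural zero for PR and remains in the denominator, so the planned rate is (1 − f) times the rate among patients whose stage can be reduced. The relative difference between the two rates is exactly f. Its size is unknown; the halving from 40% to 20% is an illustration at an assumed f of 50%, not a forecast. The identity requires f and q to be taken over the same patients, treated or evaluated.

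The consequence is limited to the interpretation of a key secondary rate. Section 10.6.2 calls all secondary objectives hypothesis generating, and PR has no target or decision rule. A reader might infer that the efficacy conclusion is compromised. It is not: 6-month CR is open to Ta-only patients, and neither the sample size nor the stopping rule in Section 10.9, which concerns progression to T2 or higher, uses PR. Nor are CR and no response the only outcomes open to these patients, since relapse with carcinoma in situ and progression are also possible.

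**What to change.** In Sections 3.2.1 and 10.6.2:

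1. Keep the PR rate over treated patients, and state how the complete-case rule defines its denominator at 3 and at 6 months.
2. Add the 3- and 6-month PR rates, with 90% Agresti-Coull intervals, among evaluated patients whose baseline stage can be reduced under Section 7.10.12.5: T1, Tis and T1+Tis. Include Ta+Tis only if the protocol states that Ta+Tis to Ta counts.
3. Show the number of Ta-only patients beside these rates.
4. Reconcile the PR examples across the synopsis, Sections 3.2, 3.2.1, 7.10.12.5 and 10.6.1, and Table 3-1, so that one list of qualifying transitions applies throughout.

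The cost is wording. Baseline stage is already collected under Section 7.5, and no new assessment is needed. The downside is a smaller denominator and a wider interval for the added rate. In the illustration above, the width grows from 29.3 percentage points (38.2 − 8.9) at 4/20 to 45.6 (64.9 − 19.3) at 4/10.
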